The primary objective of this proposal is to add to the palette of treatment options by comparing the effect of two opioid dependence treatment delivery models on improving the HIV care engagement and outcomes in Vietnam. We propose a multisite, open-label, randomized, flexible-dose noninferiority trial of buprenorphine/naloxone (BUP/NX) (n=225) versus methadone maintenance therapy (MMT) referral (n=225) for treatment of opioid dependence in HIV-infected participants in 6 Vietnam HIV clinic research sites. The study is conducted in partnership with colleagues at Hanoi Medical University (HMU), the Provincial AIDS Control (PAC) authorities of Hanoi, Thanh Hoa, and Bac Giang, the Vietnam National Institute of Mental Health, and Oregon Health & Science University.

Study sites are 4 HIV clinics in Hanoi, 1 in Thanh Hoa, and 1 in Bac Giang; epicenters of Vietnam's HIV and heroin epidemics, all of which are associated with MMT and HIV testing and counseling centers. A research coordinating center at HMU provides additional outreach, recruitment, non-medication-related study procedures and links participants to participating HIV clinic sites for clinical management. HIV providers will be trained to manage opioid dependence using BUP/NX.

Participants are HIV-infected participants with opioid dependence new to HIV care, recruited from HIV clinics, MMTs, and associated HIV testing centers. Participants randomized to BUP/NX will receive BUP/NX after successful completion of medication induction and stabilization. Participants randomized to BUP/NX will receive a taper after 12 months of study drug exposure, with referral for MMT. Participants randomized to MMT will receive usual care, which is case-manager-assisted referral to MMT. All participants receive clinic-based individual counseling and HIV care.

The primary outcome of HIV-1 viral load will be measured at baseline, 6, and 12 months. Secondary outcomes, including self-reported drug use, urine drug screens (UDS), and measures of HIV care engagement (adherence, retention) will be assessed quarterly through 12 months follow-up. Qualitative interviews with participants, family members of participants, and providers in years 1 through 4 will identify lessons-learned for scale-up of HIV clinic-based BUP/NX.

Figure 2. Study Schema

There are three specific aims in this protocol:

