Participants are randomized to clinic-based BUP/NX vs. referral for MMT. This is a non-blinded study. Randomization will be conducted by computer generated random number sequence in blocks of 10 prepared by statisticians at OHSU. Allocation assignments will be maintained in sealed, sequentially numbered envelopes by the Vietnam Research Coordinating Center (RCC) at Hanoi Medical University. HIV clinic site research assistants will call the RCC to receive allocation assignment when a participant is deemed eligible for study participation.

Pilot Data Collection and Assessments

The data collection instruments were pilot-tested with participants at four additional sites: Bac Giang PAC OPC; Bac Giang Provincial Hospital OPC; Viet Tri, Phu Tho PAC OPC; and Phu Tho Town Community Health Center OPC.

Table 2: Table of Assessments								
	Pre-Screening	Screening	Baseline	3 Month	6 Month	9 Month	12 Month	As Needed Only
Visit Window	--	60 days after Pre-Screening		+/- 14 days	+/- 14 days	+/- 14 days	-14 days/+30 days	--
Pre-Screening Consent Form	X							
Informed Consent		X						
Informed Consent Quiz		X						
Progress Note		X	X	X	X	X	X	X
Visit Checklist	X	X	X	X	X	X	X	
Locator Form	X	X	X	X	X	X	X	
Master Enrollment Log	X	X	X					
Communication Log								X
Compensation 
 • Log • Receipt 		X	X	X	X	X	X	
Data Collection Forms								
Inclusion/Exclusion Criteria (Eligibility Checklist)			X					
Pre-Screening Survey	X							
Screening Survey		X						
Baseline Survey			X					
3 Month Survey				X				
6 Month Survey					X			
9 Month Survey						X		
12 Month Survey							X	
ASI-lite Table			X	X	X	X	X	
Randomization Form			X					
Physical Exam			X					
Dosing Form 
 • BUP/NX • MMT 				X	X	X	X	
HIV Care Utilization Form				X	X	X	X	
Fatal Overdose Form								X

Table 2: Table of Assessments								
	Pre-Screening	Screening	Baseline	3 Month	6 Month	9 Month	12 Month	As Needed Only
Pregnancy and Birth Control Assessment • Includes Urine Test		X	X	X	X	X	X	
Confirmed Pregnancy Test								X
Early End of BUP/NX								X
HIV Viral Load			X		X		X	
CD4*		X*			X*		X*	
HIV genotype resistance testing (as necessary)			X				X	
HIV confirmatory testing (as necessary)		X						
HIV rapid testing	X							
Tuberculosis (PPD Skin Test)*			X*					
Hepatitis B/C*			X*					
Safety Labs* • CBC • AST/ALT •		X*						
UDS • Morphine • Methadone • Methamphetamine • Amphetamine • Buprenorphine	X	X		X	X	X	X	

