Adverse Events • Paper Log • eCRF • Serious Adverse Events eCRF								X
Protocol Deviation • Paper Log • eCRF								X

Table 2: Table of Assessments								
	Pre-Screening	Screening	Baseline	3 Month	6 Month	9 Month	12 Month	As Needed Only
Study Termination Form							X	X (if ppt ends early)
*chart abstraction possible								

Visit Procedures

Survey Data

Research assistants will administer participant surveys in a confidential setting using real-time, secure, web-based electronic data entry. All survey measures have been translated into Vietnamese and been field tested and adapted for cultural appropriateness and feasibility for electronic data collection in Vietnam during previous research.

Survey data measurements include:

- Demographics
- Drug and alcohol use
- Addiction treatment
- HIV treatment
- Co-morbid conditions including physical and mental health
- Quality of life

Medical Chart Data

Research assistants will review participant HIV clinic and MMT medical charts quarterly to inform outcome measures including receipt of ART, retention in care, and adherence to study treatment condition (buprenorphine, methadone dosing, counseling visits). Medical charts will be reviewed at Baseline to establish diagnoses of Hepatitis B, Hepatitis C, and Tuberculosis. If not available in medical chart, research staff will obtain testing as necessary.

Biologic Data

Urine samples for pregnancy and urine drug screens (morphine, methamphetamine, methadone, amphetamine, buprenorphine) will be collected and processed in the HIV clinic using point of care testing.

Viral load specimens will be drawn at baseline, 6, and 12 months, and processed for transport at HIV clinic, then transported to the National Hospital for Tropical Disease for centralized lab testing. HIV viral load testing (the primary outcome) is performed with Real-time RT-PCR on Real-time ABI 7500 machine with reagents and primers made by Invitrogen.¹¹⁰ The current viral load technique is certified for a lower limit of HIV-1 RNA detection of 55 copies/mL.

All other phlebotomy measurements (Safety Labs, and CD4) will be either drawn at the appropriate times following the above schedule or will be chart-abstracted as required. They will be drawn and processed for analysis at the HIV clinic locally.

Study physicians will conduct baseline physical exams to assess for medical appropriateness for participation.

Qualitative Data

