HIV clinic providers and staff will be trained in BUP/NX management of opioid dependence. Participants randomized to clinic-based BUP/NX will be evaluated by the HIV clinic study physician for symptoms and signs of withdrawal using clinically available opioid withdrawal scales and induced onto BUP/NX when in moderate withdrawal in order to avoid precipitated withdrawal (12-24 hours after last dose of short-acting opiates like heroin, and 2-4 days after last dose of long-acting opioids. BUP/NX induction begins with a 2-4 mg test dose followed by additional doses on the day of induction to relieve withdrawal symptoms, and then titrated to a maintenance dose between 8-24 mg/day over 1 to 3 days. Participants will return for daily dosing until a stable maintenance dose is reached, as determined clinically by the HIV clinic study physician. Dosing will remain flexible to a maximum dose of 24mg. After a participant is stabilized on a maintenance daily dose for at least 2 weeks, they may switch to every-other-day dosing (4 times per week), doubling the maintenance dose to a maximum of 32mg prior to “skip” days. Participants will continue to receive BUP/NX for 12 months, followed by a 14-day taper and referral to MMT. The study will use BUP/NX in a 4:1 ratio combination sublingual tablet for treatment of opioid dependence.

Referral for MMT

Referral for MMT has become the standard of care for opioid dependence in Vietnam. Participants randomized to MMT referral will meet with an HIV clinic case manager who will facilitate referral to MMT. Methadone dosing will be managed by MMT staff, who dispense methadone according to Ministry of Health guidelines for MMT.⁹⁸

[figure not shown]
Study sites and dosing sites

Participants will complete all research activities (consenting, surveys, and other data collection activities) at the six HIV clinics. Two HIV clinics (Tu Liem clinic and Long Bien clinic) will serve only as clinical management and medication dispensing sites, with non-medication study procedures being performed by Vietnam Research Coordinating Center (HMU) research staff.

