If a participant becomes unable to travel to the study clinic because of serious illness or injury, study staff or appointed clinic staff will be allowed to distribute buprenorphine as needed to ensure continued substance abuse treatment. Hospital or home dosing must continue to be approved on a case-by-case basis by the Principal Investigator to ensure clinical safety. Approval will also only be on a case-by-case basis to ensure that non-clinic dosing is only being used in the most serious of cases when there is no other option for a participant to remain on study drug. Current national buprenorphine guidelines allow for take-home dosing for those

unable to travel to clinic. Study staff will maintain current drug accountability procedures including completion of dosing logs and pill counts.

Figure 4. Detailed Study Flow

Risks and Benefits

Risks

In addition to the risks associated with the study medication (either arm), there are several general risks associated with participating in a clinical trial.

Risk of Underlying Conditions

Each of the participating HIV clinic research sites have established practices for managing medical emergencies, and the study staff will continue to utilize these procedures. Treatment providers at each research site will be responsible for monitoring participants for possible clinical deterioration or other problems, and for implementing appropriate courses of action. As this population will have significant ongoing health and substance use issues, events related to complications of HIV, substance use treatment or admission for substance detoxification, hospitalizations for medical and psychological reasons and deaths will be captured on study specific forms and not duplicate reported as an adverse or serious adverse event. These data will still be included in the reports to the DSMB at the regular meetings.

Risks to Confidentiality

There are also risks to confidentiality, particularly because information will be collected about substance use and abuse and other potentially illegal activities.

Phlebotomy Risks

Blood drawing may cause pain or bruising at the site and carries a small risk of infection.

Buprenorphine/Naloxone

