The primary analysis for this study will be a mixed logistic regression model comparing BUP/NX versus MMT on viral suppression rates over time. Treatment comparisons will be performed under the Intent-to-Treat (ITT) criterion; participants will be analyzed in the arm to which they

were randomized regardless of subsequent events. In this mixed logistic model, each (binary) outcome serves as a dependent variable; treatment effect (BUP/NX versus MMT referral) and time effect (e.g., baseline, 6, and 12 months) will be considered main effects. An interaction between these two main effects, e.g., treatment*time, will be included in the model. Model-fitted, marginal risk and RD estimates will be obtained at each time by applying an inverse-logit transformation to coefficients from the logistic regression model, with standard errors estimated via the delta method. We will test the primary hypothesis of noninferiority by comparing the lower bound of a 95% confidence interval to the prespecified margin (i.e., 13%); if the lower confidence limit of the RD is greater than -13%, we will conclude that the BUP/NX is noninferior to MMT. The model will include subject-level random intercepts in order to account for repeated measurements within individuals. Attrition is unavoidable in a longitudinal study; in our study, we anticipate an attrition rate of 20%. The mixed model approach is a recommended strategy for handling missing data in clinical trials under the assumption that the data are missing at random.

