We will conduct three sensitivity analyses. First, we will assume data are missing not at random and use single imputation of unsuppressed for missing VL data. Participants who are lost to follow-up will be imputed as treatment failures (i.e., not suppressed). Death from any cause and dropout will also be considered equivalent to non-suppression for the purposes of this analysis. Second, we will use multiple imputation with Markov-Chain Monte Carlo methods and “auxiliary variables” (i.e., covariates that are not part of the main analysis, but may help predict data missingness) to address missing data. We will include covariates associated with missingness at any time-points (using a relaxed p-value of 0.2) as auxiliary variables in our multiple imputation model. Finally, for our third sensitivity analysis, we will conduct a per-protocol analysis among participants who received at least one dose of study medication in the 90 days before each visit. If sensitivity analysis results change the primary outcome findings, we will report the results alongside our main analysis.

Secondary outcomes including binary ART initiation, ART adherence, and retention in HIV care will be analyzed using similar procedures. As these are superiority hypotheses, we will test them using two-tailed tests at an alpha level of .05.

Aim 2: Assess effect of clinic-based BUP/NX versus MMT referral on opioid use in HIV-infected participants with opioid dependence.

- **H2:** We hypothesize that participants randomized to BUP/NX will have a lower proportion of positive assessments for opioid use (self-report + UDS) at 12 months versus MMT referral

Overview. In Aim 2, we assess the effect of clinic-based BUP/NX on opioid use as measured by urine drug screens or any self-reported use in the last 30 days, assessed at 3, 6, 9, and 12 months following randomization.

Dependent variables. The primary dependent variable for Aim 2 will be the proportion of positive assessments for opioid use at 12 months, as measured by any self-reported opioid use or positive urine drug screen during the 12-month follow-up assessment (binary). We will consider secondary substance use outcomes including proportion of follow-up visits with a positive assessment for opioid use (proportion), and other illicit drug use (binary), and alcohol use (binary).

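### The per-protocol rule neither requires the assigned arm's drug nor excludes the other arm's drug, so the check can keep the crossover already present in the ITT analysis

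*Combined protocol and SAP*

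**What the plan says.** The Aim 1 Data Analysis Plan tests noninferiority in an ITT mixed logistic model. The lower 95% limit for the risk difference (RD, BUP/NX minus MMT) is compared with -13 points. Three sensitivity analyses follow, and in the third "we will conduct a per-protocol analysis among participants who received at least one dose of study medication in the 90 days before each visit". Sensitivity results are promised next to the main result only if they change the finding.

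The term study medication is not defined. These places bear on it:

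- Risks and Benefits, Risks, uses it for both treatments: "the risks associated with the study medication (either arm".
- Objectives uses the similar term study drug for BUP/NX alone: "Participants randomized to BUP/NX will receive a taper after 12 months of study drug exposure, with referral for MMT".
- Medical Chart Data collects, each quarter, "adherence to study treatment condition (buprenorphine, methadone dosing, counseling visits".
- Referral for MMT places methadone outside the study's own dispensing: "Methadone dosing will be managed by MMT staff, who dispense methadone according to Ministry of Health guidelines for MMT".

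Table 2 has a form titled "Early End of BUP/NX" and dosing forms for both drugs at 3, 6, 9 and 12 months. No rule for switchers and no expected switching rate appears.

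**The concern.** An ITT analysis keeps switchers in the arm to which they were randomized. If one treatment is worse and its participants move to the other, the arms come to look alike, and in a noninferiority trial that can pass for success. A per-protocol analysis is the usual check, but it works only if it removes the switchers.

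Switching from BUP/NX to methadone is foreseeable. The protocol calls MMT referral the standard of care, and every site is affiliated with MMT programs that can accept new referrals. No comparable route from MMT to BUP/NX is described. If the per-protocol set keeps switchers in the arm they left, its agreement with ITT says little. Because the result is shown alongside only when it differs, a check diluted in the same way as ITT might not be shown there at all.

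**Working it through.** **Reading the rule.** There are three possible meanings of study medication.

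1. *BUP/NX only.* Almost nobody in the MMT arm would qualify and there would be no comparison, so the term has to cover methadone.
2. *Either drug.* A participant who left BUP/NX months ago and now takes methadone has a qualifying dose and stays in the BUP/NX group.
3. *The assigned drug only.* Long-standing switchers drop out. A participant whose last BUP/NX dose was, say, 80 days before the visit, and who has been on methadone since, still qualifies.

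Readings 2 and 3 both keep some crossover. They differ in how much.

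**The plan's own figure.** The per-protocol rule carries none. The nearest is the original sample size in Power Analysis (50% against 65%, two-sided 5%, 80% power):

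n = [1.96·√(2×0.575×0.425) + 0.8416·√(0.5×0.5 + 0.65×0.35)]² / 0.15² = (1.370 + 0.582)² / 0.0225 ≈ 169.3, so 170 per arm and 340 in total, as stated.

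**Inputs for the illustration**

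- From the documents: margin 13 points; 50% suppression in the MMT referral group; 225 per arm less 20% attrition, 225 × 0.8 = 180.
- Assumed: true RD of exactly -13 points in those who stay on BUP/NX; a share s of the BUP/NX per-protocol set on methadone; switchers' suppression d points from MMT, with d = 0 at first.

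**Formulas** (normal approximation, unpooled variance; p0 = MMT rate, p1 = BUP/NX rate in the set)

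- RD = (1 - s)(-13) + s·d
- SE = √[p0(1 - p0)/180 + p1(1 - p1)/180]
- P(lower limit > -13) = Φ[(RD + 13)/SE - 1.96]

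**Switchers do as well as MMT (d = 0)**

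| s | RD (points) | SE (points) | (RD + 13)/SE | Chance of showing noninferiority |
|---|---|---|---|---|
| 0 | -13.0 | 5.18 | 0 | 2.5% |
| 10% | -11.7 | 5.20 | 0.250 | 4.4% |
| 20% | -10.4 | 5.21 | 0.499 | 7.2% |
| 30% | -9.1 | 5.23 | 0.746 | 11.2% |

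With 225 per arm the last three chances are 4.6%, 8.0% and 13.0%. With an assumed MMT rate of 80% and 180 per arm they are 4.7%, 8.3% and 13.7%.

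**Varying how switchers do (s = 20%, 180 per arm, MMT 50%)**

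| Switchers against MMT | RD (points) | Chance |
|---|---|---|
| equal | -10.4 | 7.2% |
| 13 points below (same as stayers) | -13.0 | 2.5% |
| 30 points below | -16.4 | 0.4% |

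If stayers truly equal MMT and 20% switch with suppression 30 points below MMT, keeping them gives RD = 0.2 × (-30) = -6. The chance of showing noninferiority is then 27%, against 64% with them removed (144 against 180).

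**The case against.** **The wording.** A reader might infer that the plan accepts a dose from either arm. It does not say so. The phrase in the Risks section can mean the medication of whichever arm a participant is in, and it does not define an analysis set. Per-protocol ordinarily implies the allocated treatment, and the chart review is framed around the assigned condition. This stands: the either-drug reading is possible but not stated. It does not remove the gap, because the assigned-drug reading still admits recent switchers.

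**The direction.** A reader might infer that the check is always biased towards noninferiority. The second table shows otherwise: that needs switchers to do better than those who stay. People who end BUP/NX early could plausibly do worse. This also stands.

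**The inputs.** The 50% is for everyone referred to MMT, including any who never start methadone. The 180 is an attrition figure, not a per-protocol count. The early-end form shows that stopping is recorded, not that people switch. The percentages are therefore illustrations.

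**Baseline.** The model's "time effect (e.g., baseline, 6, and 12 months) will be considered main effects", and nobody has had study treatment at baseline, so a reader might infer that the rule deletes nearly all baseline records. An analyst would sensibly take each visit to mean follow-up visits. A clarifying phrase is enough.

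**Removing switchers has its own risk.** Suppose the overall BUP/NX deficit is 13 points (37% suppressed) and the 20% who switch are suppressed at 20%. Stayers are then at (37 - 0.2×20)/0.8 = 41.25%, and the RD without switchers is -8.75. With 144 against 180 the SE is 5.54 points, and Φ(4.25/5.54 - 1.96) is about 12%. This stands as a limit of any per-protocol analysis, and it is why the result should be read beside ITT and not in place of it.

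**Conclusion.** The concern holds in a limited form. As written, the rule does not require the assigned drug and does not exclude other-arm dosing, so the check can keep the crossover that is already in the ITT result. If BUP/NX is truly 13 points worse and switchers do as well as MMT, the check's false-noninferiority chance rises from 2.5% to between 4.4% and 11.2% for 10% to 30% switching. Under other assumptions about switchers the effect is nil or reversed. The documents give no switching rate, so the actual size is unknown.

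A reader might also infer that these are error rates for the trial's conclusion. They are not: noninferiority is decided on the ITT model, which keeps switchers as randomized under any per-protocol wording, and the per-protocol analysis is not a condition for the claim. What is weakened is its value as a check. Since the trial is unblinded, the definition should be settled before outcomes by arm are examined.

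**What to change.** Replace the rule in the Aim 1 Data Analysis Plan with one to this effect:

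- Per-protocol records are the 6- and 12-month visits at which the participant received the assigned arm's medication in the preceding 90 days and no dose of the other arm's medication in that period.
- Methadone started after the planned 12-month BUP/NX course and taper does not count as other-arm medication. Without this, an adherent completer referred to MMT and seen late in the 12-month window (up to +30 days) would be dropped.
- Baseline records are kept for every participant included.
- The number of switchers is reported by arm, and the per-protocol result is shown next to the ITT result whether or not it differs.

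The BUP/NX and MMT dosing forms and the quarterly MMT chart review already supply the data, so the change is to the text only. The cost is a smaller per-protocol set, a wider interval for that analysis, and post-randomization selection, which the report should acknowledge.

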Power Analysis: Since our primary outcome in this aim is opioid use, the power analysis is based on this outcome. With our proposed sample size (450 as the total, 225 for each treatment arm), we have gained the power of 91% to detect 15% in difference between the two groups at

the level of alpha 0.05, provided that the proportion of UDS positive for opioid at 12 months will be 65% for MMT referral. This power analysis is conservative due to not maximizing multiple-time-point data from our longitudinal study. We anticipate the power is much higher to off-set the complexity of the mixed logistic model (adjusting for some covariates) we propose in the data analysis plan (see below).

Data Analysis Plan: The primary (binary) outcome for Aim 2 is opioid use, collected at baseline, 3, 6, 9, and 12 months. We will use an approach as in Aim 1.

Aim 3: Assess BUP/NX implementation experience to inform national scale-up of clinic-based BUP/NX.

Overview. We will conduct qualitative interviews with HIV providers, administrators, and opioid dependent participants, and their family members in participating HIV clinics annually during years 1 through 4 to document and describe formative implementation strategies, challenges, and best practices. Results inform policy-making for national scale-up of clinic-based BUP/NX in Vietnam.

Qualitative Procedures and Analysis. The implementation aim documents the experience of providers and participants at clinics to further inform adoption of BUP/NX in Vietnam and guides planning efforts and policy-making. Data also monitor the performance of the sites and qualitative interviews provide critical detail for enhanced understanding of the findings from the trial (Aim 1 and 2). Using the Taxonomy of Mixed Method Designs¹³⁴⁻¹³⁶, our design has a QUAN +Qual structure with simultaneous data collection and emphasis/weight placed on the quantitative efforts. The qualitative data provide complementary information to illuminate and expand the findings from Aims 1 and 2.

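### The Aim 2 outcome combines urine screens with unblinded self-report, and the analysis plan specifies no urine-only analysis, so a disclosure difference between arms could create or hide an H2 effect

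*Combined protocol and SAP*

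**What the plan says.** All references are to the combined protocol and SAP.

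- **Outcome.** Data Analysis, Aim 2, Dependent variables, defines the primary variable as opioid use at 12 months "as measured by any self-reported opioid use or positive urine drug screen during the 12-month follow-up assessment (binary"). The Aim 2 Overview gives the self-report window: "as measured by urine drug screens or any self-reported use in the last 30 days".
- **Other substance-use outcomes in that section.** These are "proportion of follow-up visits with a positive assessment for opioid use (proportion), and other illicit drug use (binary), and alcohol use (binary"). The first repeats the same composite by visit. The others do not concern opioids.
- **Analysis.** For Aim 2 the plan says "We will use an approach as in Aim 1". Under Aim 1 it says "We will conduct three sensitivity analyses": missing counted as failure, multiple imputation, and per-protocol. None separates the components of the opioid outcome.
- **Where urine appears alone.** The Objectives section lists self-reported drug use and urine drug screens as separate secondary outcomes assessed quarterly, but gives no model. The Aim 2 power paragraph claims 91% power for a 15-point difference, "provided that the proportion of UDS positive for opioid at 12 months will be 65% for MMT referral".
- **Conduct.** The Randomization section states "This is a non-blinded study", and site research assistants obtain the allocation by telephone. Under Survey Data, research assistants administer the surveys in a confidential setting. Study sites and dosing sites says "Participants will complete all research activities (consenting, surveys, and other data collection activities) at the six HIV clinics", then adds that at two of the six clinics coordinating-centre staff perform the non-medication procedures.

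**The concern.** In an either/or outcome, a positive urine screen overrides a denial. A negative screen does not, so a urine-negative participant who used in the last 30 days counts as positive only if he or she says so. Interviewers and participants know the allocation, and nothing in the design ensures that disclosure is equal in the two arms.

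H2 is a superiority claim. If BUP/NX participants disclose less, the composite shows a benefit that is not there. If they disclose more, a real benefit is diluted. Urine is the component that does not depend on disclosure. It is already scheduled at 3, 6, 9 and 12 months, and its rate is the one used for power. Unless its analysis is fixed in advance, whether and how it is shown can be decided after the composite result is known.

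**Working it through.** **1. The plan's own figure.** Inputs from the Aim 2 power paragraph: 225 per arm, 65% versus 50%, alpha 0.05, taken as two-sided.

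- Pooled SE = √(2 × 0.575 × 0.425 / 225) = 0.0466. Unpooled SE = √((0.65 × 0.35 + 0.50 × 0.50) / 225) = 0.0461.
- Power = Φ((0.15 − 1.96 × 0.0466) / 0.0461) = 89.9%, or 90.3% with the unpooled SE throughout. This agrees with the stated 91% to within about a point.
- After the plan's 20% attrition (225 × 0.8 = 180 per arm), the pooled version gives 82.4%.

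Because 65% is stated as a urine-positive rate, this is already the power of a urine-only comparison.

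**2. False difference from unequal disclosure.** The following quantities are assumptions; the documents give none of them except that 65% is the plan's MMT urine rate.

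- b = urine-positive share, equal in both arms (no true effect)
- x = share of all participants who used in the last 30 days but are urine-negative
- d_M, d_B = fraction of those who disclose on MMT and on BUP/NX

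Composite rate = b + x·d in each arm, so the false difference is D = x(d_M − d_B). It cannot exceed x. The chance of a significant result favouring BUP/NX is Φ(D/SE − 1.96), with SE = √((p_M(1−p_M) + p_B(1−p_B)) / 180).

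| b | x | d_M | d_B | Composite MMT / BUP/NX | D (points) | SE | Chance of false benefit |
|---|---|---|---|---|---|---|---|
| 65% | any | 80% | 80% | equal | 0 | n/a | 2.5% |
| 65% | 5% | 80% | 60% | 69.0 / 68.0% | 1.0 | 0.0490 | 4% |
| 50% | 5% | 100% | 75% | 55.0 / 53.75% | 1.25 | 0.0525 | 4% |
| 65% | 10% | 80% | 50% | 73.0 / 70.0% | 3.0 | 0.0476 | 9% |
| 65% | 15% | 80% | 50% | 77.0 / 72.5% | 4.5 | 0.0457 | 16% |
| 65% | 20% | 80% | 50% | 81.0 / 75.0% | 6.0 | 0.0436 | 28% |
| 50% | 15% | 100% | 50% | 65.0 / 57.5% | 7.5 | 0.0512 | 31% |
| 50% | 20% | 100% | 50% | 70.0 / 60.0% | 10.0 | 0.0500 | 52% |

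Worked row (x = 15%, gap 30 points): 0.045 / 0.0457 = 0.98; 0.98 − 1.96 = −0.98; Φ = 16%. The base rate also matters: with b = 65% in place of 50%, the last two rows become 39% and 67%.

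**3. The reverse direction.** Suppose the urine rates truly are 65% (MMT) and 50% (BUP/NX) and x = 15% in both arms.

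- Disclosure 80% in both arms: composite 77% versus 62%, SE 0.0479, power Φ(0.15/0.0479 − 1.96) = 88%.
- Disclosure 50% on MMT and 80% on BUP/NX: composite 72.5% versus 62%, difference 10.5 points, SE 0.0492, power Φ(0.105/0.0492 − 1.96) = 57%.

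**4. What a urine-only model can use.** The inclusion criteria require an opioid-positive urine screen. Table 2 schedules urine at pre-screening, screening and months 3, 6, 9 and 12, but not at baseline. A baseline level would therefore be positive for every participant by design and would add nothing to a logistic model.

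**The case against.** Several points on the other side stand.

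- **Urine is not absent from the plan.** The Objectives section names it as a quarterly secondary outcome. A reader might infer that the objective component was dropped altogether; that is too strong. What is missing is its specification in the Aim 2 analysis plan.
- **No direction is documented.** A reader might infer that BUP/NX participants are the ones likely to under-report, because they report at the clinic that treats them. No passage links reported use to loss of treatment. Both arms receive HIV care and counselling at the clinic, both give urine there, and MMT participants are referred by a clinic case manager. More frequent contact on BUP/NX could as easily raise disclosure.
- **The setting is mixed.** Methadone is managed by MMT staff, but the documents do not say that the HIV clinics dispense only BUP/NX. The sites are associated with MMT programmes and co-location is not ruled out. Coordinating-centre staff and the confidential setting are partial safeguards.
- **The either/or rule limits the damage** to urine-negative users.
- **Urine alone is not a clean arbiter.** It looks back less than 30 days, so a real fall in intermittent use might show mainly in self-report. Brief abstinence before a visit, or urine missing unequally by arm, could also distort it.

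These points rule out any claim that H2 is biased in a known direction or by a known amount. They do not supply the missing analysis.

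**Conclusion.** The point holds as a gap in specification that affects what H2 can conclude. The plan defines a composite, powers it with a urine rate, names urine as an outcome elsewhere, and then specifies no urine-only analysis for Aim 2.

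The possible effect runs from none to serious. For a false BUP/NX benefit it is 2.5% with equal disclosure, about 4% with small gaps and 16% to 52% with large ones; the most extreme pattern reaches 67% at the plan's 65% urine rate. A gap the other way could cut power from 88% to 57% in the example shown. All of this rests on assumed disclosure rates and an assumed share of urine-negative users, and nothing in the documents selects among the rows. None of the figures is an estimate for this trial. Only Aim 2 is affected; the viral-load primary outcome does not depend on self-report.

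**What to change.** Keep the composite as the primary Aim 2 outcome and add the following to the Aim 2 Data Analysis Plan:

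1. A supportive intention-to-treat analysis of the morphine screen alone at 12 months, using the Aim 2 mixed logistic approach fitted to months 3, 6, 9 and 12, without a baseline level. Naming the analyte matters because the panel also includes methadone and buprenorphine, and the outcome definition does not say which results count as positive.
2. An absent urine result is missing, not negative.
3. The urine result is reported beside the composite whatever either shows, with self-report/urine discordance tabulated by arm.
4. If the two disagree, the report says that the composite finding rests on self-report, and that differential reporting or the shorter urine look-back could explain it.

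The cost is one extra model and one table on data already collected, with no added participants: power at 65% versus 50% is about 82% with 180 per arm. The limit is that urine covers less than 30 days, so this analysis supports the composite and does not replace it.
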